#### 2.7.2.2 Participants who lack mental capacity

Participants may lack capacity following the cardiac arrest. This may be temporary or permanent.

If the participant lacks capacity to make a decision about ongoing trial participation, the researcher will approach a personal consultee who meets the criteria described in the Mental Capacity Act 2005. The researcher will provide information about the trial, as well as the participant information sheet and a cover letter. The consultee will be given adequate time to review the information sheet and an opportunity to ask questions. The consultee will be asked to consider what decision the participant is likely to have made if they had mental capacity.

If no personal consultee is available, or a potential personal consultee is unwilling to take on this role, researchers will approach a professional consultee who is not connected with the conduct of the trial. The same process, as described for the personal consultee, will be followed.

The consultee may decide it is not an appropriate time to discuss the trial or they may decide that the participant would not want to take part in which case their feelings will be respected and their decision about taking part will be recorded.

If an initial approach is made to a professional consultee and a personal consultee subsequently becomes available, then the opinion of the personal consultee will be sought. This will override any decision made by the professional consultee.

The consultee's opinion regarding the participant's likely views on the collection of routine data and patient-reported outcome measures will be recorded on a signed form, counter-signed by the staff member receiving the opinion. This form may be signed physically or electronically as described above, however where neither of these are possible a verbal opinion may be recorded by the staff member and witnessed by one other person.

If an initial approach is made to a personal or professional consultee and the participant subsequently regains capacity prior to hospital discharge, then the participant's consent will be sought. This will override any opinion given by the personal or professional consultee.

If a participant who has previously given their consent to continue in the study loses capacity, we will continue to collect the primary outcome data from their routine health records (permission

for this will be sought as part of the HRA CAG application), but we will not approach them further to complete follow-up questionnaires at 3 and 6 months following the cardiac arrest. If they regain capacity subsequently, we will seek their consent to continue in the study and proceed according to their wishes.

#### 2.7.3 Approaching patients or their consultee following discharge

In rare circumstances, participant consent or a personal/ professional consultee opinion may not be obtained before hospital discharge.

If this occurs, a researcher at the hospital site from which the patient was discharged will contact the participant or their consultee (if it is known that the participant lacks mental capacity) at their home address to seek consent or an opinion. Where possible, the initial contact will be made by post or email to allow time for the patient or consultee to consider their willingness to be contacted. This will be followed by a phone call and second contact if no reply is received. Up to three contact attempts will be made within 28 days of the first contact. The researcher will use available systems to determine correct contact information and, where appropriate, to ensure the participant is still alive. Where available, more than one system will be accessed to determine survival status.

If the participant or their consultee does not respond to this contact within 28 days of the first contact, then we will assume that they do not agree to collection of further routine data or patient-reported outcome measures. We will include only data collected up to that point in the study analysis.

#### 2.7.4 Patients who do not survive

Following careful consideration with our PPI advisors, the relatives of those who do not survive to ICU discharge will not be informed of trial participation. It is felt the burden (further distress) outweighs the benefit (transparency) since the treatments under study are both part of standard clinical practice and are used routinely during IHCA. Relative-focused information sheets will be developed to enable us to respond to those who may request further information about the trial. This model, developed and agreed with our patient and public advisors, is based on several previous similar large-scale trials that have successfully enrolled cardiac arrest patients both inside and outside hospital.

#### 2.8 Randomisation

#### 2.8.1 Randomisation

The randomisation algorithm will be provided by Warwick Clinical Trials Unit (WCTU). A computergenerated randomisation sequence will be created, stratified by hospital site and time of day (8am to 6pm or outside of these hours). Time of day is included as a stratification variable because out-ofhours cardiac arrests tend to have less favourable outcomes (42). Patients will be randomised 1:1 to SGA or TI. Randomisation will take place using a bespoke mobile phone progressive web application (PWA), which will be developed by the programming team at WCTU. The PWA will function asynchronously (off-line) to address any problems with data connectivity that may exist in participating hospitals, and to ensure there is no delay in the randomisation process. If the patient is deemed eligible pressing a single button on screen will immediately display the allocation, and irrevocably enrol the patient. If, due to a technical or other failure, the PWA does not display an allocation within five seconds the patient will be treated according to usual care and the clinical judgement of the cardiac arrest team. If, despite technical failure, the allocation is recorded by the PWA the patient will be included in the study under the "intention to treat" principle, whereas if no allocation is recorded the patient will not be included in the study. Following the IHCA a small additional amount of non-identifiable patient data will be entered to the PWA by the enrolling clinician and automatically uploaded to WCTU. WCTU will then alert the research team at that hospital site for patient identification and follow-up. Preparatory work by the trial team including interviews and simulations has demonstrated that this approach is clinically and technically feasible; it will be tested further during the internal pilot study.

#### 2.8.2 Post-randomisation withdrawals, exclusions and moves out of region

Post randomisation exclusions may be authorised by the trial management group and approved by the Trial Steering Committee if a participant is randomised in error. However, if a participant is randomised and later found to be ineligible they will still be included in the trial and analysed under the principle of "intention to treat". Similarly, patients who are randomised but do not receive the allocated intervention (for example they achieve a return of spontaneous circulation (ROSC) after randomisation but before advanced airway management is attempted) will be retained and analysed in the group to which they were assigned. In making any decision to exclude after randomisation care will be taken to avoid introducing bias (42).

Participants may cease trial follow-up at any time without prejudice. Unless a participant who has previously consented to continuing data collection explicitly ceases their participation, they should be followed-up wherever possible and data collected as per the protocol until the end of the trial.

If at any point following consent the patient (or their consultee) indicates that they no longer wish to participate usual care will continue to be provided. This will be logged on the database from the point they cease participation, and no further contact will be made. All non-identifiable data collected up to that point will be retained and included in the analysis. If the patient (or their consultee) indicates that they wish to be withdrawn from the study, no further data will be collected and no further contact will be made. All non-identifiable data collected prior to consent and the primary outcome will be retained and included in the analysis.

# 2.9 Trial treatments / intervention

#### 2.9.1 Trial treatment(s) / intervention

Intervention: A **supraglottic airway device** of the type used routinely in that hospital. During resuscitation the SGA will be placed according to manufacturer's instructions, with end-tidal carbon dioxide monitoring wherever possible, following an initial period of bag-mask ventilation as required. If a functioning SGA has already been placed at the point of randomisation, and the patient is randomised to SGA, this device may be left in situ. Two attempts at SGA placement should be made. An attempt is defined as introducing a SGA past the teeth, and concludes when the SGA is removed from the mouth. If two attempts at SGA placement are unsuccessful treatment will proceed as dictated by the treating clinician (including tracheal intubation if indicated). If successful, the SGA should be used until resuscitation efforts cease or return of spontaneous circulation (ROSC) is achieved for >20 minutes, at which point further management will proceed as dictated by the treating clinician.

Comparator: **Tracheal intubation.** During resuscitation tracheal intubation should occur, with endtidal carbon dioxide monitoring wherever possible, following an initial period of bag-mask ventilation as required. If a functioning SGA has already been placed at the point of randomisation, and the patient is randomised to tracheal intubation, the SGA should be removed, and tracheal intubation attempted. Two attempts at intubation should be made. An attempt is defined as introducing the laryngoscope past the teeth and concludes when the laryngoscope is removed from the mouth, regardless of whether or not a tracheal tube is inserted. If two attempts at tracheal intubation are unsuccessful subsequent treatment will proceed as determined by the treating clinician (including placement of a SGA if indicated). If successful, tracheal intubation should continue until resuscitation efforts cease or ROSC is achieved for >20 minutes, at which point further management will proceed as dictated by the treating clinician.

Both interventions are part of standard clinical care in the treatment of IHCA and there are no known additional risks to the participants above routine care.

#### 2.9.2 Compliance/contamination

Treatment fidelity will be closely monitored and assessed throughout the pilot study. We will obtain feedback from sites and enhance all processes to ensure that the delivery of both interventions is as protocolised as possible. A set of standardised training materials will be developed to meet the needs of all staff involved in the trial. In the event of evidence of non-compliance, this will be flagged to the site research team. The site research team will then investigate events through discussion with the clinical team and, where appropriate, will report this as a non-compliance. Where necessary, further training and support will be provided.

Contamination due to crossover: crossovers will lead to contamination of the initial randomised intervention due to a mixing of effects in the outcomes, reducing the power of the study. This is further complicated by the fact that crossover may be a selective process whereby patients who have their treatment switched have a different prognosis compared with those who do not. Crossover will be monitored and training provided to sites to trouble-shoot issues related to crossover where necessary. The impact of crossover on the statistical power of the trial is discussed further in the statistical analysis section (section 6.0).

#### 2.10 Methods to minimise bias

#### 2.10.1 Concealment and blinding

Treatment allocation will be concealed prior to randomisation using a bespoke, computerised randomisation PWA. Screening logs will be assessed to examine reasons why patients have not been enrolled into the study.

The majority of outcomes are objective and will not be influenced by knowledge of treatment allocation. It will not be possible to blind clinical team members to treatment allocation following randomisation. Blinding of the wider clinical team and site research team will be limited as cardiac arrest team members may document treatment allocation in the patient's medical record. Patients will be blinded because they are in cardiac arrest and unconscious when the allocated airway management occurs. Site teams will be encouraged to maintain blinding by not informing patients or their relatives of their treatment allocation, unless the participant or consultee states a specific wish to be informed.

#### 2.10.2 Unblinding

There is no requirement for unblinding procedures due to the open-label nature of the trial.

#### 2.11 Co-enrolment into other trials

Co-enrolment with other trials will be reviewed on a case-by-case basis in accordance with national NIHR-supported co-enrolment guidelines. There are many current examples of successful co-enrolment between UK critical care studies, facilitated by these guidelines and supported by co-enrolment agreements.

# 2.12 International recruitment

Patients may be recruited in hospitals internationally, subject to the research governance and ethics committee approvals required in each participating country. This is supported by University of Warwick acting as a co-sponsor. Variations to this protocol relevant to each recruiting country are described in accompanying appendices.

#### 2.13 End of trial

The trial will end when all participants have completed their 6-month follow-up, or receipt of routinely collected data, whichever is later.

The trial will be stopped prematurely if:

- Mandated by the Ethics Committee
- Following recommendations from the Data Monitoring Committee (DMC) and/or Trial Steering Committee (TSC)
- Funding for the trial ceases

The Research Ethics Committee will be notified in writing within 90 days when the trial has been concluded or within 15 days in the event of early termination of all trial related activities.

### 3. METHODS AND ASSESSMENTS

#### 3.1 Schedule of delivery of intervention and data collection

Table 1 describes the trial assessments and timepoints for data collection.

Visit	1	2	3	4
Visit Window (No. Weeks 🗆 No. Days)	Baseline	Hospital Discharge (or 30 days post randomisation)	3 calendar months ( 🗆 🗆 weeks) After V 1	6 calendar months (□ 4 weeks) After V 2
Informed consent		*		
Inclusion/exclusion criteria				
Randomisation				
Intervention				
Modified Rankin Scale score				
Quality of Life (EQ-5D-5L)				
Adverse events				
Resource utilisation				
Other**				

Table 1Trial assessments

\*Once participants have recovered sufficiently (usually around the time of discharge from the Intensive Care Unit) and whilst they are still in hospital, a member of the hospital research team will approach the patient (or if they lack capacity a consultee) to explain the study and seek consent to continue in the trial.

\*\*Other and unscheduled events, such as co-enrolment and NHS National Data Opt Out, may be collected at other timepoints.

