#### **TRIAL SUMMARY**

Trial Title	Randomised trial of the clinical and cost effectiveness of					
	during in-hospital cardiac arrest (AIRWAYS-3)					
Internal ref. number (or short title)	AIRWAYS-3					
Trial Design	A multi-centre, open-label, pragmatic, individually randomised, parallel group, superiority trial and economic evaluation to determine the clinical and cost effectiveness of a supraglottic airway (SGA) versus tracheal intubation (TI) during in-hospital cardiac arrest (IHCA). The trial will include an internal pilot to confirm feasibility					
Trial Participants	Adult (known or believed to be age >=18) hospital inpatients will be eligible for randomisation if they receive resuscitation following IHCA that requires a 2222 call and advanced airway management					
Planned sample size	4190 participants from centres throughout the UK and internationally					
Treatment Duration	Until return of spontaneous circulation (ROSC) for >20 minutes or resuscitation efforts cease, after which the airway will be managed by the attending team as they feel appropriate					
Follow-up Duration	6-months post IHCA					
Planned Trial Period	1 st January 2022 – 31 st December 2026					
Trial Objectives	
 
(1) Conduct an internal pilot study to confirm the feasibility of the large-scale multi-centre trial
 
(2) Determine the clinical effectiveness of SGA management, for adults with in-hospital cardiac arrest, in terms of survival with a favourable functional outcome and health-related quality of life.
 
(3) Estimate, in an integrated economic evaluation, the cost-effectiveness of SGA compared with TI
 
					
Primary Outcome Measure	Functional status at hospital discharge (or 30 days post- randomisation whichever is shorter) as measured by the modified Rankin Scale (mRS)					
Secondary Outcome Measures	
 
Initial ventilation success
 
Regurgitation/aspiration during resuscitation
 
Return of Spontaneous circulation (ROSC) >20 minutes
 
					

	
 
ICU and hospital length of stay
 
					
	Health-related quality of life at discharge, 3 and					
	6 months)					
	• Survival to hospital discharge, 3 months and 6					
	months					
	
 
Functional status (mRS) at 3 and 6 months
 
					
Economic outcomes	Additional unscheduled care and re-admissions					
	(to 6 months)					
	
 
In-hospital stay utilisation and cost
 
					

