#### 2.3.1 Efficacy

Primary: Modified Rankin Scale (mRS) score assessed at hospital discharge (or at 30 days post-randomisation if the participant remains in hospital).

Secondary:

• Initial ventilation success (visible chest rise with end tidal carbon dioxide monitoring consistent with successful ventilation (where measured) immediately after insertion of a supraglottic airway device or tracheal tube;

• Regurgitation during the resuscitation attempt (stomach contents seen in the patient's pharynx, mouth or nose), and whether this occurred before, during or after advanced airway management;

• Aspiration during the resuscitation attempt (stomach contents seen below the vocal cords, inside a correctly placed tracheal tube or the airway channel of a correctly placed supraglottic airway device), and whether this occurred before, during or after advanced airway management;

- Return of spontaneous circulation (ROSC) for at least 20 minutes;
- Intensive Care Unit length of stay;
- Hospital length of stay;
- Survival to hospital discharge, 3 and 6 months;
- Functional outcome (mRS) score at 3 and 6 months;

• Health-related quality of life at discharge or 30 days (whichever occurs sooner), 3 and 6 months.

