### 3.2.3 Long term follow-up assessments

Consistent with the core outcome set recommendations, health related quality of life will be measured using EQ-5D-5L at discharge/30 days, 3 and 6 months. mRS will also be measured at 3 and 6 months. The EQ-5D-5L captures the timespan over which functional/neurological recovery tends to plateau (43). It is less burdensome to complete than other tools, is freely available, accessible in multiple languages and may be completed by the patient or a proxy. It comprises five dimensions: mobility; self-care; usual activities; pain/discomfort; anxiety/depression. Each dimension has 5 levels: no problems; slight problems; moderate problems; severe problems; extreme problems. From the EQ-5D-5L health utilities will be calculated for all participants, using standard tariffs. A £15 voucher will be given to every participant who completes a questionnaire at 3 months, and again at 6 months, to acknowledge their contribution to the study.

Longer-term follow up: data will be obtained from NHS England Hospital Episode Statistics (for further Emergency Department attendances and hospital admissions up to 6 months post randomisation), the National Cardiac Arrest Audit (for mRS at discharge or 30 days and length of hospital stay) and the Case Mix Programme National Clinical Audit for adult intensive care (for length of ITU stay) to enable efficient, long-term follow-up of patients. Follow-up for post discharge functional outcomes and health related quality of life will be coordinated by the WCTU and use an established system for contacting patients or their personal consultee to ensure effective follow up (rates > 98% in previous studies) (34,35).

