#### 6.6 Health Economic Evaluation

A prospectively planned economic evaluation will be conducted from an NHS and personal social services perspective using NICE Reference Case approach (47). Resource use will include intervention, hospital (ICU, HDU and ward days) and community costs (primary care and social care costs) in the 6 months following randomisation. Resources will be costed using national reference unit costs where available, reflated to current prices. A secondary societal perspective will additionally include time lost from work (paid/unpaid) and patient borne health costs (e.g. wheelchair by type, home adaptations, feeding aids, walking aids, home-help, support from relatives). Health-related quality of life (EQ-5D-5L) responses will be used to generate quality-adjusted life years (QALYs) using the valuations recommended by NICE and using the area-under-the curve (AUC) method.(48,49) Baseline

EQ-5D-5L values will be set to reflect the unconscious health state minimising potential bias in the QALY AUC calculation.(50,51) Within-trial analysis (to 6 months) using bivariate regression of costs and QALYs will inform a probabilistic assessment of incremental treatment cost-effectiveness. Missingness mechanisms will be explored and multiple imputation methods used where appropriate to avoid biases associated with complete case analysis (52-54). Within-trial findings, reflecting the outcomes and prognosis of patients at 6 months, will inform a lifetime decision-analytic model. Modelling will draw upon best available information from the literature to supplement the trial data. Parameter uncertainty in the decision-analytic model will be explored using probabilistic sensitivity analysis. Longer term costs and consequences will be discounted to present values at 3.5% per annum. Sensitivity analyses will be undertaken to explore uncertainty and to consider issues of generalisability of the study. Presentation of findings for the within-trial analysis and model will include incremental cost-effectiveness ratio planes, incremental net monetary benefit, cost-effectiveness acceptability curves and value of information.

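### Table 1 counts the 6-month visit from discharge or day 30, while every section that names an origin for the 6-month point counts from the arrest or randomisation

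*Protocol*

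**What the plan says.** Table 1 in Protocol Section 3.1 lists four visits. Visit 2 is headed "Hospital Discharge (or 30 days post randomisation". Visit 3, at 3 calendar months, is timed "weeks) After V 1", that is, from baseline. Visit 4, at 6 calendar months, is timed "4 weeks) After V 2". Section 2.3.1 bounds V2, because the primary outcome is "assessed at hospital discharge (or at 30 days post-randomisation if the participant remains in hospital". V2 therefore falls between day 0 and day 30.

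Four other places give an origin for the 6-month point:

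- Trial Summary, follow-up duration: "6-months post IHCA".
- Section 2.7.2.2, on participants who lose capacity: "follow-up questionnaires at 3 and 6 months following the cardiac arrest".
- Section 3.2.3, on Hospital Episode Statistics (HES): "hospital admissions up to 6 months post randomisation".
- Section 6.6, on resource use: "in the 6 months following randomisation".

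Other places, including Sections 2.3.1, 5.1 and 6.2.3.3, refer to 3 and 6 months without saying from when.

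**The concern.** Two consecutive follow-up visits run on different clocks, and the protocol gives no reason. Patients are randomised during the resuscitation attempt, so arrest and randomisation are in practice the same origin. V2 is not: it is a post-randomisation date that varies by patient.

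Two things are at stake if Visit 4 is scheduled as Table 1 says. First, the 6-month mRS and EQ-5D-5L, both secondary outcomes, would be measured at a time since arrest that depends on time to discharge, and hospital length of stay is itself a secondary outcome. If stay differed by arm, so would the time of assessment. Second, EQ-5D-5L feeds an area-under-the-curve QALY that Section 6.6 analyses jointly with costs. Costs stop 6 months after randomisation, whereas the last utility could be measured nearer 7 months.

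**Working it through.** The protocol states no figure for the size of this shift, so there is none to reproduce. The sample size of 4,190 does not depend on it.

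**Inputs.** V2 on day 0 to 30 after randomisation (Sections 2.3.1 and 3.1). Visit 3 = V1 + 3 calendar months and Visit 4 = V2 + 6 calendar months (Table 1). The symbol before the 4-week window is not legible in the text available; I assume plus or minus, so 28 days either side.

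**Formulas.**

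- Shift = (V2 + 6 months) − (V1 + 6 months)
- Visit 4 target day = (V2 + 6 months) − randomisation date
- Visit 3 to Visit 4 gap = (V2 + 6 months) − (V1 + 3 months)
- Latest day in window = maximum Visit 4 target day + 28

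Calendar months differ in length, so each quantity was computed for every randomisation date in one year (2023) and is given as a range.

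| V2 on day | Shift, days (mean) | Visit 4 target day | Visit 3 to 4 gap, days | Latest day in window |
|---|---|---|---|---|
| 0 | 0 (0) | 181-184 | 90-92 | 212 |
| 5 | 3-8 (5.0) | 186-189 | 95-100 | 217 |
| 14 | 12-17 (14.0) | 195-198 | 104-109 | 226 |
| 30 | 28-33 (30.1) | 211-214 | 120-125 | 242 |

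The first row is also what every survivor would have if Visit 4 were anchored to V1, whatever the length of stay.

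**Worst case as a share of the horizon.** 30 / 183 = 16%, for a patient still in hospital at day 30.

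**Does the window absorb it?** For a patient still in hospital at day 30, the two target dates are 28 to 33 days apart against a half-window of 28 days. A questionnaire completed exactly 6 months after the arrest would then usually fall outside Table 1's own window. For shorter stays the two windows overlap enough to include both targets.

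**How many patients.** Only survivors complete these questionnaires. Section 6.1 assumes about 10% survive to discharge: 0.10 × 4,190 = 419, fewer after later deaths, non-consent and non-response.

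**The case against.** The best defence is that V2 is a slip for V1 and nobody schedules from it. Section 2.7.2.2 refers to the same questionnaires and counts from the arrest. Post-discharge follow-up is coordinated centrally by the trials unit (Section 3.2.3), so one correct date in its system would prevent the problem. Under the assumed window, a visit made on the V2-based target would still lie within 4 weeks of the V1-based target for discharges up to about day 28. The shift touches roughly a tenth of participants. A patient who dies before either target date scores 6 on the mRS on both clocks. Using actual assessment dates in the QALY calculation is ordinary analysis-plan detail.

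Most of this limits the consequence and does not remove the contradiction. Table 1 is the protocol's schedule of assessments, and both anchors in it are legible. Under Appendix A, Finnish research nurses make their own 3- and 6-month calls, so scheduling is not in one pair of hands.

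A reader might infer more than the protocol supports:

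- **That 6-month outcomes are being taken late.** Nothing shows that the V2 clock is in use.
- **That 6-month survival is mistimed too.** Section 6.2.3.3 takes survival from the national audit, site data and HES, and the Table 1 rows list no survival assessment.
- **That all other text contradicts Table 1.** Several sections name no origin; the statement holds only for those that do.
- **That the arms would be biased against each other.** The protocol gives no length-of-stay figures by arm, so differential timing is a possibility without an estimate.

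**Conclusion.** The contradiction is certain; its consequence is conditional. If Visit 4 is scheduled from Table 1, survivors' 6-month mRS and EQ-5D-5L move later by their time to V2: about 5 days for a 5-day stay, 14 for a 14-day stay, and about 30 at most. Timing would then follow a post-randomisation outcome, and costs and the last utility would end at different times. The cap of about 30 days rests on V2 being discharge or day 30, whichever comes first. The comparison of windows rests on reading the window as plus or minus 4 weeks. The primary outcome, the sample size and survival are not affected, and the protocol gives no basis for computing a bias in mRS, utility or QALYs. This is an internal inconsistency in the working schedule that should be corrected, and it does not threaten the main result.

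**What to change.** Change the Visit 4 header in Table 1 so that the 6 calendar months run from V1, matching the Trial Summary and Sections 2.7.2.2, 3.2.3 and 6.6. Confirm that the trials unit's scheduler and the Finnish sites both set the 3- and 6-month contacts from the randomisation date. For any Visit 4 already made on the V2 clock, use actual days since randomisation in the QALY area under the curve. If the V2 anchor was intended, the protocol should say why, and those four places must be reconciled with it instead. The recommended change costs one table cell and a check of the scheduling date. It adds no visits, no patient burden and no change to the sample size.
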